Study Protocol

Study Title:

To investigate the potential effectiveness of mirror-aided cross-education using the innovative 'Mirror Strengthening Device' compared to mirror therapy alone in post-stroke upper limb recovery: A pilot randomised feasibility study.

Document creation date: February 4th 2022

NCT number [not yet assigned].

Identifiers: [NCT ID not yet assigned]

Study Protocol

To investigate the potential effectiveness of mirror-aided cross-education using the innovative 'Mirror Strengthening Device' compared to mirror therapy alone in post-stroke upper limb recovery: A pilot randomised feasibility study.

Study Objectives:

1. To conduct a randomised controlled pilot feasibility study to examine the effects of mirror-aided cross-education using a specially designed Mirror Strengthening Device in post stroke upper limb recovery.
2. To examine the feasibility of mirror-aided cross-education using a specially designed Mirror Strengthening Device in this patient cohort
3. To investigate any adverse effects of mirror-aided cross-education using a specially designed Mirror Strengthening Device in this population.

Study Design:

The Design is an assessor blinded, randomised control pilot feasibility trial. The independent assessor, who is blinded to the treatment assignment, will perform all the assessments. After baseline measurements are obtained, the patients will be randomly assigned to the intervention or control group using computer generated block random numbers where gender and function will be considered. A statistician who will be blinded to the research protocol and not otherwise involved in the trial will conduct the random number programme.

Setting:

Assessments: Exercise Physiology Lab, IT Sligo.

Intervention: Participants own home.

Intervention:

Both groups will perform a 5 minute warm up, 5 minute cool down and main set of exercises consisting of up to 4 sets of 5 repetitions of 5 dynamic shoulder exercises.

They will be instructed to perform the concentric and eccentric phases of the contraction at 3 seconds and 4 seconds, respectively, rest for 2 sec between contraction and rest between sets. The full set should take approximately 30mins.

Participants will be asked to complete the intervention 5 days a week for 4 weeks.

Experimental Group:

The experimental group will be performing the repetitions with a set resistance on the Mirror Strengthening Device

Control Group:

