The control group will be performing the repetitions with no resistance on the Mirror Strengthening Device.

Positioning:

Participants will be seated in a chair in front of their own kitchen table. The elbow is flexed at 90 degrees and kept in close to the trunk not resting on anything. Palm of hand is facing the exercise device and holding a pulley. The untrained limb will be positioned in a similar position to the training limb supported on the table behind the exercise device with the shoulder slightly flexed forward to allow this positioning.

Participants will view the mirror reflection of their less- affected limb in the mirror which is positioned lateral to the mid-sagittal plane of the more - affected limb before any strength training commences.

The participant will be asked to look at the reflected image of their less-affected limb in the mirror as they train. They will then complete the prescribed HEP.

Rests:

Participants will be informed that breaks can be taken during the training session for reasons of tiredness or fatigue if required.

Training Diary:

All participants will be provided with a training diary. They will be asked to completed this before and after each training session.

Adverse Effects:

All participants will be asked to record any changes before and after each training session in the HEP record book and to contact Principal Researcher with any adverse effects.

Outcome Assessments:

Outcome Measures will be taken before and after the 4-week home exercise programme and at 3 months follow up and will include:

Primary:

Isokinetic Strength: (Biodex System 4 Pro with advantage software)

Grip Strength: (Hand held dynamometer)

Secondary:

Fugl-Meyer Upper Extremities Test

Stroke Impact Scale

Modified Ashworth Scale (MAS) for spasticity).

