## Statistical Analysis

We will analyse the data using Excel and SPSS for Windows. Paired T tests will be used to compare before and after data in both groups.

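### The only analysis in the supplied SAP text is raw within-arm change; a baseline-adjusted arm difference should be the main result

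*SAP*

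**What the plan says.** The SAP, under Statistical Analysis, names the software and then a single test: "Paired T tests will be used to compare before and after data in both groups". The supplied text contains no covariate, no model and no estimate of the difference between arms.

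The Protocol describes a design that would support more. Under Study Design: "The Design is an assessor blinded, randomised control pilot feasibility trial". The baseline is fixed before allocation: "After baseline measurements are obtained, the patients will be randomly assigned to the intervention or control group". Allocation uses "computer generated block random numbers where gender and function will be considered". Under Outcome Assessments: "Outcome Measures will be taken before and after the 4-week home exercise programme and at 3 months follow up". The primary outcomes are isokinetic strength and grip strength, both continuous. The secondary outcomes are the Fugl-Meyer upper-extremity test, the Stroke Impact Scale and the Modified Ashworth Scale. The study title frames the question as a comparison with mirror therapy alone.

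**The concern.** Every participant has a pre-randomisation value of each outcome, but the stated analysis uses it only by subtraction. Two consequences follow.

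First, a paired test asks whether an arm changed. It does not ask whether the device changed it. Recovery over the four weeks, practice on the tests and any regression to the mean all count as change in that arm. The concurrent control arm is there to remove what is common to both, and the stated test does not use it.

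Second, the title's question can be answered only by comparing arms. If paired changes are all that is reported, readers will compare raw changes or the two p-values. A contrast of raw changes fixes the slope on baseline at 1. With equal SDs and rho below 1 this over-corrects, so the arm that happened to start weaker appears to gain more. The contrast also usually has a larger error variance than a model that estimates the slope. For a pilot, what is at stake is the effect estimate and interval that would inform a later trial.

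**Working it through.** The documents state no sample size, power, SD or correlation, so there is no figure to reproduce. All numbers below are illustrative.

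**Inputs**
- From the SAP: paired t test, before against after, in both groups.
- From the Protocol: two randomised arms, baseline measured before allocation, follow-up after 4 weeks and at 3 months.
- Assumed: equal SDs at both times (set to 1), rho of 0.5, 0.7 and 0.9, and 5, 10 or 20 per arm.

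**1. What the paired tests can show.** Suppose both arms gain 0.4 SD and there is no arm difference. In 20,000 simulated trials with 10 per arm, an arm's paired test was significant at two-sided 5% in about 21%, 31% and 71% of trials at rho 0.5, 0.7 and 0.9. Exactly one arm was significant in 33%, 43% and 41%. With 20 per arm this was 48%, 48% and 6%. As a check, 2p(1-p) with p = 0.206 gives 2 x 0.206 x 0.794 = 0.327. A result in one arm only is therefore no evidence of a device effect.

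**2. Chance imbalance in a contrast of raw changes.** Given a baseline difference D between arms, the expected difference in change is shifted by -(1-rho) x D. The simulated slopes agreed: about -0.50, -0.30 and -0.10 at rho 0.5, 0.7 and 0.9. The standard error of D under simple randomisation with 10 per arm is sqrt(2/10) = 0.447 SD. A one-standard-error imbalance then shifts the contrast by:
- rho 0.5: 0.5 x 0.447 = 0.22 SD
- rho 0.7: 0.3 x 0.447 = 0.13 SD
- rho 0.9: 0.1 x 0.447 = 0.04 SD

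The chance that D exceeds 0.5 SD in either direction is 26%, 11% and 5% with 10, 20 and 30 per arm, again under simple randomisation.

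**3. Precision in large samples.** The error variance is 2(1-rho) for change and 1-rho^2 for ANCOVA, so the ratio of ANCOVA to change is (1+rho)/2:
- rho 0.5: 0.75
- rho 0.7: 0.85
- rho 0.9: 0.95

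**4. Precision in small samples.** ANCOVA spends one degree of freedom and must estimate the slope. With n per arm, the CI width ratio (ANCOVA to change) is sqrt((1+rho)/2) x sqrt(1+1/(2n-4)) x t(2n-3)/t(2n-2), using 97.5% quantiles.
- n = 10: sqrt(1+1/16) = 1.031 and t(17)/t(18) = 1.004, product 1.035.
- n = 5: sqrt(1+1/6) = 1.080 and t(7)/t(8) = 1.025, product 1.108.

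| rho | sqrt((1+rho)/2) | CI ratio, 10 per arm | CI ratio, 5 per arm |
|---|---|---|---|
| 0.5 | 0.866 | 0.896 | 0.959 |
| 0.7 | 0.922 | 0.954 | 1.021 |
| 0.9 | 0.975 | 1.009 | 1.080 |

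ANCOVA narrows the interval at moderate rho. It widens it slightly when rho is high and the arms are very small.

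**The case against.** The strongest reply is that steps 2 to 4 describe a between-arm contrast of change scores, which the supplied text does not plan. Within one arm, centring on that arm's own baseline mean returns the same mean change, so a baseline covariate would gain nothing there. This stands. A reader might infer that the planned paired tests are themselves shifted by baseline imbalance, or that missing adjustment is a fault independent of the missing arm comparison. The documents support neither. The shift and the precision loss arise only once arms are compared, as the title requires.

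Other limits also stand:
- Individual regression to the mean averages out in an arm's mean unless participants were selected for extreme values, and the supplied text gives no strength-based selection rule. Where it does occur, it is the control comparison that removes the shared part, not the covariate alone.
- Under randomisation a change-score contrast is unbiased overall. The shift is conditional on the imbalance that occurs.
- Considering gender and function in allocation may make strength imbalance less likely than the simple-randomisation figures suggest.
- A reader might infer that adjustment gains precision at every rho below 1. The small-sample table shows otherwise.
- Part of the SAP was not available for review, so the absence of adjustment is established only for the supplied text.

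The reply does not rescue the plan. Adding an unpaired test of change scores would supply the arm comparison but leave the imbalance shift in place.

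**Conclusion.** The point holds in a bounded form. In the supplied text, raw within-arm change is the sole analysed quantity and the pre-randomisation baseline is never a covariate. As written, the analysis cannot isolate the device effect from change common to both arms. A comparison built from its results would carry (1-rho) times any chance imbalance, which is 0.04 to 0.22 SD for a one-standard-error imbalance at 10 per arm and rho 0.9 to 0.5. Precision would usually be lost too, though not always: at 5 per arm the ANCOVA interval is about 2% wider at rho 0.7 and 8% wider at rho 0.9. These sizes rest on equal SDs and on assumed rho and arm size. The imbalance figures also assume simple randomisation. The sponsor should make the change, but in a pilot feasibility trial this is an improvement to the effect estimate and does not invalidate the study.

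**What to change.** In the SAP, Statistical Analysis, replace the paired t tests as the main analysis. For isokinetic strength, grip strength, Fugl-Meyer and Stroke Impact Scale, fit a linear model of the post-programme (4-week) value on arm, with that outcome's own baseline value as covariate. Repeat the model for the 3-month value. Report each baseline-adjusted arm difference with its 95% CI, labelled as an exploratory pilot estimate. Keep the within-arm before and after means as description only. The Modified Ashworth Scale is ordinal and falls outside this linear model.

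The cost is a few lines of SAP text. The data are already to be collected, and SPSS, the software the SAP names, can fit the model. Statistically it costs one degree of freedom, with a possible slight loss of precision if the arms are very small and rho is high.
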